**Novo Nordisk**

## **2.1 Injection area**

The trial products IDeg, IDet and IAsp should be injected subcutaneously into the thigh, upper arm (deltoid area) or the abdomen. The chosen region should be the same throughout the trial. Rotation of injection sites within a given region is recommended.

## **2.2 Time of injection**

Insulin degludec should be administered OD any time of the day, preferably at the same time every day.

Subjects receiving IDet OD should administer the dose any time of the day, preferably at the same time each day. Subjects receiving IDet BID should administer one dose in the morning and the other dose in the evening or at bedtime.

Insulin aspart should be administered 2-4 times daily with the meals. Additional bolus dosing is allowed at the investigator's recommendation.

## **3 Initiation and titration**

### **3.1 Initiation**

Subjects randomised to IDeg should reduce their previous basal insulin dose by 20% and dose OD.

Subjects randomised to IDet should be transferred unit-to-unit. If the subjects switch from an OD regimen, they should continue on an OD regimen. If the subjects switch from a BID regimen they should continue on a BID regimen. Dose reduction should be considered.

The subjects should have their bolus insulin doses switched to IAsp unit-to-unit.

### **3.2 Basal titration**

After randomisation the basal insulin doses should be adjusted once weekly by the investigator in connection with the scheduled visits/phone contacts.

The IDeg dose adjustment should be based on the mean of three pre-breakfast SMPG values measured on two days prior to titration and on the day of the visit. This also applies to subjects receiving IDet OD.

For subjects receiving IDet BID, the morning dose will be adjusted according to the mean pre-main evening meal SMPG values obtained on the three days prior to the day of the visit or contact. The evening dose will be adjusted according to the mean pre-breakfast SMPG values measured on the

Protocol Appendix A  
 Trial ID: NN1250-4300  
 UTN: U1111-1191-3018  
 EudraCT no.: 2017-000048-17

**CONFIDENTIAL**

Date: 17 December 2020  
 Version: 4.0  
 Status: Final  
 Page: 5 of 7

**Novo Nordisk**

two days prior to the day of the visit or contact and on the day of the visit or contact. Adjustments will be in accordance with [Table 3–1](#) and [Table 3–2](#).

If one or more SMPG values are missing, the dose adjustment should be performed on the remaining SMPG value(s). The insulin dose adjustment should aim to reach an SMPG of 4.0-5.0 mmol/L (71-90 mg/dL).

The dose calculation will be based on the most recent dose taken within the last three days before the contact.

**Table 3–1 IDeg or IDet dose increase**

Mean pre breakfast or pre-main evening meal SMPG		Dose adjustment
mmol/L	mg/dL	U
4.0 – 5.0	71 – 90	No adjustment
5.1 – 10.0	91 – 180	+2
10.1 – 15.0	181 – 270	+4
> 15.0	> 270	+6

If one of the SMPG values is below target of 4.0 mmol/L (71 mg/dL) the insulin dose should be reduced according to [Table 3–2](#).

**Table 3–2 IDeg or IDet dose reduction**

Lowest pre-breakfast or pre-main evening meal SMPG		Dose adjustment
mmol/L	mg/dL	U
<3.1	<56	-4
3.1 – 3.9	56 – 70	-2

### 3.3 Bolus titration

Insulin aspart adjustments should be at the investigator’s discretion and in collaboration with the subject.

During pregnancy it is recommended to measure SMPG values 60 minutes after main meal start. These values can be used for further bolus dose optimisation. The American College of Obstetricians and Gynecologists and American Diabetes Association recommend a 60 minutes post-prandial SMPG  $\leq 7.8$  mmol/L ( $\leq 140$  mg/dL).

Protocol Appendix A  
Trial ID: NN1250-4300  
UTN: U1111-1191-3018  
EudraCT no.: 2017-000048-17

**CONFIDENTIAL**

Date: 17 December 2020  
Version: 4.0  
Status: Final  
Page: 6 of 7

**Novo Nordisk**

### 3.4 Deviations from the algorithm

It is recommended that the algorithm is followed. However, it is also important that the decision to adjust the IDeg or IDet doses is based on all relevant information as described in Section [1](#). A reason for deviating from the algorithm should be entered into the eCRF.

## 4 Data collection

The following data should be entered into the eCRF within 24 hours (on weekdays) after each site visit or phone contact:

- Per protocol SMPG values
- Doses of IDeg/IDet taken the last three days before the contact
- New prescribed dose of IDeg/IDet at the contact
- Reason(s) for deviation(s) from the titration algorithms, if any
- Hypoglycaemic episode(s)

## 5 Review procedure

Surveillance of titration data will be performed centrally by Novo Nordisk in an unbiased manner. It is important that data regarding dose titration is entered into the eCRF within 24 hours (on weekdays). If delays occur, action cannot be taken in due time before the subject's next site visit or phone contact. The aim is to reduce the time periods in which a subject may receive suboptimal treatment.

The data listed in Section [4](#) will be reviewed by Novo Nordisk within 24 hours (on weekdays). The reviewer may contact the investigator to get clarification regarding the reason for deviation or to request entry of missing data.

When the investigator receives an inquiry, a response should be received at Novo Nordisk within 24 hours (on weekdays).

During the trial, HbA1c will be monitored by Novo Nordisk for additional surveillance of the glycaemic control. Novo Nordisk may be in contact with sites (visit or phone contact) to discuss progress in glycaemic control and titration of individual subjects based on SMPGs and HbA1c. This will be done in an unbiased and whenever possible in a blinded manner.

Protocol Appendix A  
Trial ID: NN1250-4300  
UTN: U1111-1191-3018  
EudraCT no.: 2017-000048-17

CONFIDENTIAL

Date: 17 December 2020  
Version: 4.0  
Status: Final  
Page: 7 of 7

Novo Nordisk

**CONFIDENTIAL**

Date: 17 December 2020  
Version: 4.0  
Status: Final  
Page: 1 of 3

**Novo Nordisk**

## **Interview questions for baseline hypoglycaemic episodes**

### **Instructions to interviewer (do not read aloud to the subject):**

- Please read the questions as written. However, you may rephrase if subject needs clarification.
- If the subject gives a range for a response (e.g. experienced 2 to 4 severe hypoglycaemic episodes), record the average of the response (3 times). If the average is a decimal number (3.5 times), then round down to the nearest integer (3 times) and record this number.
- If a subject changes her response, record the last response given.
- If the subject responds to a question by saying something like “I do not know, I never really think about it”, ask the subject to take a minute and think about it.
- If the subject still does not remember or refuses to answer, please do not complete the question (leave the field blank).

### **Instructions to the subject (read aloud to the subject):**

- The following questions are about your experience with hypoglycaemic episodes (low blood sugar levels).
- Please answer to the best of your recollection.
- Please try to think of the last 6 months for the first question and the last 4 weeks for the second question.
- Perhaps you experienced no symptoms, but noted the low blood sugar episode when measuring your blood sugar, possibly for another reason.

Protocol Appendix B  
Trial ID: NN1250-4300  
UTN: U1111-1191-3018  
EudraCT no.: 2017-000048-17

~~CONFIDENTIAL~~

Date: 17 December 2020  
Version: 4.0  
Status: Final  
Page: 3 of 3

**Novo Nordisk**

## General questions

1. In the last **6 months** have you had a hypoglycaemic event from which you couldn't recover yourself and you needed help from someone else to recover, i.e. a 'severe hypoglycaemic event'?

No (if no, go to question 2)

Yes (ask the following questions)

a) How many? \_\_\_\_\_

b) How many of these events occurred at night (between midnight and 6 o'clock in the morning)?  
\_\_\_\_\_

2. In the last **4 weeks** have you had a hypoglycaemic event which you have been able to manage yourself, i.e. a 'non-severe hypoglycaemic event'?

No

Yes (ask the following questions)

a) How many? \_\_\_\_\_

b) How many of these events occurred at night (between midnight and 6 o'clock in the morning)?  
\_\_\_\_\_

**CONFIDENTIAL**

Date: 27 January 2021  
 Version: 2.0  
 Status: Final  
 Page: 2 of 34

**Novo Nordisk**

## Version history

This Statistical Analysis Plan (SAP) for trial NN1250-4300 is based on the final protocol version 4.0 dated 17DEC2020.

**Table 1 SAP Version History Summary**

SAP Version	Approval Date	Change	Rationale
1	See ETMF	Not Applicable	Original version
2	See ETMF	Flowchart removed	Flowchart should not be included

Statistical Analysis Plan  
Trial ID: NN1250-4300  
UTN: U1111-1191-3018  
EudraCT No: 2017-000048-17

~~CONFIDENTIAL~~

Date: 27 January 2021  
Version: 2.0  
Status: Final  
Page: 6 of 34

Novo Nordisk

# 1 Introduction

## 1.1 Objectives and endpoints

### 1.1.1 Objectives

#### Primary objective

To compare the effect on glycaemic control of IDeg once daily (OD) plus IAsp 2-4 times daily with meals and IDet OD or twice daily (BID) plus IAsp 2-4 times daily with meals in a population of pregnant women with T1DM.

#### Secondary objectives

- To compare the effect on maternal safety of IDeg OD plus IAsp 2-4 times daily with meals and IDet OD/BID plus IAsp 2-4 times daily with meals in a population of pregnant women with T1DM.
- To compare the effect on pregnancy outcome of IDeg OD plus IAsp 2-4 times daily with meals and IDet OD/BID plus IAsp 2-4 times daily with meals in a population of pregnant women with T1DM.

### 1.1.2 Endpoints

#### 1.1.2.1 Primary endpoint

Last planned HbA1c prior to delivery after gestational week (GW) 16.

This primary endpoint was chosen as it was not considered feasible to collect an HbA1c sample at delivery. Therefore, the primary endpoint is evaluated at last planned visit prior to delivery after GW 16. Gestational week 16 has been chosen as the earliest assessment of the primary endpoint, as some subjects, e.g. those randomised as pregnant, may not attend a site visit prior to GW 16.

#### 1.1.2.2 Secondary endpoints

##### Supportive secondary endpoints

###### Supportive maternal efficacy endpoints

- HbA1c ≤ 6.0% (42 mmol/mol) from last planned HbA1c prior to delivery after GW 16 (yes/no)
- HbA1c ≤ 6.5% (48 mmol/mol) from last planned HbA1c prior to delivery after GW 16 (yes/no)
- Last planned average post-prandial glucose (PPG) prior to delivery after GW 16
  - Average of three main meals

Statistical Analysis Plan  
Trial ID: NN1250-4300  
UTN: U1111-1191-3018  
EudraCT No: 2017-000048-17

~~CONFIDENTIAL~~

Date: 27 January 2021  
Version: 2.0  
Status: Final  
Page: 7 of 34

**Novo Nordisk**

- Last planned fasting plasma glucose (FPG) prior to delivery after GW 16

#### Supportive maternal safety endpoints

The pregnancy period is defined as the period from the first day of pregnancy (date of conception) or randomisation (whichever comes last) to the date of delivery. The first day of pregnancy is calculated from the estimated gestational age from the ultrasound scan made before or at randomisation (visit 2) for subjects randomised pregnant and before or at visit 55 for subjects randomised non-pregnant and becoming pregnant in the conception period of the trial. For subjects with delivery prior to the ultrasound scan, the first day of pregnancy is determined by the investigator based on the estimated gestational age at time of delivery.

Two different baselines will be applied; a treatment baseline and a pregnancy baseline. For all subjects the treatment baseline is defined as the latest available measurement at or before randomisation (visit 2). For subjects randomised pregnant the pregnancy baseline is derived from the treatment baseline, and the two baseline values will be identical. For subjects randomised non-pregnant and becoming pregnant in the conception period of the trial, the pregnancy baseline corresponds to data from visit 55.

- Number of hypoglycaemic episodes during the pregnancy period (from first day of pregnancy (date of conception) or randomisation (whichever comes last) to delivery)
- Development of sight-threatening retinopathy defined as proliferative retinopathy or maculopathy from treatment baseline as well as from pregnancy baseline to the end of treatment visit (yes/no)
- Number of adverse events during the pregnancy period (from first day of pregnancy (date of conception) or randomisation (whichever comes last) to delivery)
- Pre-eclampsia defined as new-onset hypertension (blood pressure  $\geq 140$  mmHg systolic or  $\geq 90$  mmHg diastolic, based on at least 2 measurements taken at least 4 hours apart) occurring from GW 20 to delivery and simultaneous proteinuria (defined as  $\geq 300$  mg protein in a 24 hours urine sample, a protein-to-creatinine ratio of  $\geq 300$  mg/g in a urine sample or a urine dipstick protein of 1+) or presence of eclampsia, HELLP syndrome, or other severe organ involvement (yes/no)
- Mode of delivery, e.g. vaginal, operative vaginal, planned caesarean section or unplanned caesarean section, induced or spontaneous delivery
- Change in body weight from pregnancy baseline to last planned visit before delivery (kg)

Statistical Analysis Plan  
Trial ID: NN1250-4300  
UTN: U1111-1191-3018  
EudraCT No: 2017-000048-17

~~CONFIDENTIAL~~

Date: 27 January 2021  
Version: 2.0  
Status: Final  
Page: 8 of 34

**Novo Nordisk**

### Supportive pregnancy outcome endpoints

- Birth weight (g)
- Pre-term delivery (delivery < 37 completed GWs) (yes/no)
- Early foetal death (delivery < 20 completed GWs) (yes/no)
- Perinatal mortality (death of foetus/infant between  $\geq 20$  completed GWs before delivery and < 7 completed days after delivery) (yes/no)
- Neonatal mortality (death of infant between  $\geq 7$  completed days after delivery and < 28 completed days after delivery) (yes/no)
- Presence of major abnormalities (classified according to EUROCAT) (yes/no)
- Live born infants (yes/no)
- Number of adverse events in the infant from day of delivery to final follow-up
- Neonatal hypoglycaemic episodes defined as plasma glucose  $\leq 1.7$  mmol/L (31 mg/dL) during the first 24 hours after birth or  $\leq 2.5$  mmol/L (45 mg/dL) between 24 hours and 48 hours after birth (yes/no)

#### 1.1.2.3 Exploratory endpoints

Cord blood IDeg levels in live born infants.

#### 1.1.2.4 Other assessments

- Change in clinical evaluations from treatment baseline as well as from pregnancy baseline to the end of treatment visit in terms of:
  - Vital signs (including blood pressure and pulse)
  - Physical examinations
- Change in central laboratory assessments from treatment baseline as well as from pregnancy baseline to the end of treatment in terms of:
  - Haematology (haemoglobin, haematocrit, erythrocytes, thrombocytes, leucocytes)
  - Biochemistry (creatinine, alanine aminotransferase (ALT), aspartate aminotransferase (AST), alkaline phosphatase (AP), sodium, potassium, albumin, total bilirubin)
- Basal insulin dose from pregnancy baseline to the end of treatment visit

Statistical Analysis Plan  
Trial ID: NN1250-4300  
UTN: U1111-1191-3018  
EudraCT No: 2017-000048-17

~~CONFIDENTIAL~~

Date: 27 January 2021  
Version: 2.0  
Status: Final  
Page: 9 of 34

Novo Nordisk

## 1.2 Trial design

- Trial population :

Number of subjects planned to be screened: 306

Number of subjects planned to be randomised: 214

It is expected that approximately  $\frac{1}{3}$  of the subjects are to be randomised as non-pregnant and  $\frac{2}{3}$  of the subjects are to be randomised as pregnant.

- Trial phase : 3b
- Trial design : This is a randomised (1:1), open-label, parallel, multi-centre, multi-national, treat-to-target (TTT), comparing the effect and safety of IDeg OD plus IAsp 2-4 times daily with meals with IDet OD/BID plus IAsp 2-4 times daily with meals in pregnant women with T1DM.
- Subjects will be randomised either non-pregnant with the intention to become pregnant or pregnant from GW 8-13 + 6 days.
- Stratification : Randomisation will be stratified according to the pregnancy status at time of randomisation as well as planned continued use of the subject's own continuous glucose monitoring (CGM) device.
- Treatment : Eligible subjects will be randomised 1:1 in an open-label manner to one of the below treatment regimens:
  - IDeg OD + IAsp 2-4 times daily with meals, or
  - IDet OD/BID + IAsp 2-4 times daily with meals
- Trial duration : The duration of the trial depends on the time of conception relative to the time of enrolment and delivery as summarised schematically in [Figure 1-1](#) and [Figure 1-2](#). The total trial duration for the subject will depend on whether the subject is randomised non-pregnant or pregnant and will be maximum 25 months as summarised in [Table 1-1](#).

Statistical Analysis Plan  
 Trial ID: NN1250-4300  
 UTN: U1111-1191-3018  
 EudraCT No: 2017-000048-17

[figure not shown]
**CONFIDENTIAL**

Date: 27 January 2021  
 Version: 2.0  
 Status: Final  
 Page: 10 of 34

**Novo Nordisk**

**Table 1–1 Trial duration for subjects**

Period	Non-pregnant subjects	Pregnant subjects
Screening	V1, up to three weeks before randomisation	
Randomisation	V2	
Treatment	Up to 53 weeks for conception. If the subject becomes pregnant, trial treatment furthermore continues throughout the pregnancy until end of treatment 28 days after delivery. If the subject does not become pregnant end of treatment will be 7 days after V54.	Throughout the pregnancy period. Trial treatment continues until end of treatment 28 days after delivery.
Follow-up period	The trial will end with two follow-up contacts (P91 and V92) 7 and 30 days after end of treatment respectively.	

If the subject becomes pregnant at any time during the 52 weeks conception period of the trial, their next visit will be the V54D visit (if applicable) or V55 visit. If the subject does not become pregnant in the conception period of the trial, the EOT visit will be completed 1 week after V54. Abbreviations: IDeg = insulin degludec, IDet = insulin detemir, IAsp = insulin aspart, OD = once daily, BID = twice daily, FDP = first day of pregnancy, V55 = pregnancy baseline visit, EOT = end of treatment (V90), FU1/FU2 = follow-up contacts 1 (P91) and 2 (V92).

[figure not shown]
**Figure 1–1 Trial design for subjects who are non-pregnant at randomisation.**

Statistical Analysis Plan  
Trial ID: NN1250-4300  
UTN: U1111-1191-3018  
EudraCT No: 2017-000048-17

~~CONFIDENTIAL~~

Date: 27 January 2021  
Version: 2.0  
Status: Final  
Page: 11 of 34

**Novo Nordisk**

Abbreviations: IDeg = insulin degludec, IDet = insulin detemir, IAsp = insulin aspart, OD = once daily, BID = twice daily, V2 = pregnancy baseline visit, EOT = end of treatment (V90), FU1/FU2 = follow-up contacts 1 (P91) and 2 (V92).

**Figure 1–2 Trial design for subjects who are pregnant at randomisation.**

Further details are described in the [protocol section 5](#).

Statistical Analysis Plan  
Trial ID: NN1250-4300  
UTN: U1111-1191-3018  
EudraCT No: 2017-000048-17

~~CONFIDENTIAL~~

Date: 27 January 2021  
Version: 2.0  
Status: Final  
Page: 12 of 34

**Novo Nordisk**

## 2 Statistical hypotheses

Formally, let  $D$  be the mean treatment difference (IDeg-IDet) in ‘Last planned HbA1c prior to delivery after GW 16’. The null-hypothesis of IDeg being inferior by 0.4% or more will be tested against the alternative hypothesis of NI (IDeg inferior by less than the NI-limit) as given by:

$$H_0: D \geq 0.4\% \text{ against } H_A: D < 0.4\%$$

Non-inferiority will be considered confirmed if the upper bound of the two-sided 95% CI for  $D$  (mean treatment difference in HbA1c) is strictly below 0.4%. This is equivalent to using a one-sided test of size 2.5%.

## 3 Sample size determination

Refer [protocol section 17.1](#).

Statistical Analysis Plan  
 Trial ID: NN1250-4300  
 UTN: U1111-1191-3018  
 EudraCT No: 2017-000048-17

**CONFIDENTIAL**

Date: 27 January 2021  
 Version: 2.0  
 Status: Final  
 Page: 13 of 34

**Novo Nordisk**

## 4 Analysis sets

**Table 4–1 Overview of subject analysis sets**

Subject Analysis Set	Description
Full analysis set for all women (FASall)	Includes all randomised women. Subjects in the FAS all will contribute to the evaluation “as randomised”.
Safety analysis set for all women (SASall):	Includes all randomised women exposed to at least one dose of trial product. Subjects in the SAS all will contribute to the evaluation “as treated”.

**Table 4–2 Overview of defined analysis sets**

Defined Analysis Set	Description
Full analysis set for pregnant women (FASpregnant)	Includes all randomised women who are pregnant during the trial. Subjects in the FAS pregnant will contribute to the evaluation “as randomised”.
Per protocol analysis set for pregnant women (PPpregnant)	Includes subjects from FAS pregnant who: 
 
• Have not violated any inclusion criteria
 
• Have not fulfilled any exclusion criteria
 
• Are exposed to trial drug at least the first four weeks after randomisation or, in case of termination of pregnancy within the first four weeks after randomisation, until time of termination of pregnancy.
 
 Subjects in the PP pregnant analysis set will contribute to the analysis according to the treatment received prior to potential discontinuation of randomised treatment. This will be referred to as contributing to the evaluation “as treated”.
Safety analysis set for pregnant women (SASpregnant)	Includes all randomised women exposed to at least one dose of trial product and who are pregnant during the trial. Subjects in the SAS pregnant will contribute to the evaluation “as treated”.

The primary endpoint and secondary efficacy endpoints are analysed using full analysis set for all pregnant women.

Statistical Analysis Plan  
 Trial ID: NN1250-4300  
 UTN: U1111-1191-3018  
 EudraCT No: 2017-000048-17

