## 17.4.2 Safety endpoints

### 17.4.2.1 Classification of Hypoglycaemia in subjects

Treatment emergent: hypoglycaemic episodes will be defined as treatment emergent if the onset of the episode occurs on or after the first day of trial product administration, and no later than 7 days from the last day on trial product.

Nocturnal hypoglycaemic episodes: episodes occurring between 00:01 and 05.59 both inclusive.

Hypoglycaemic episodes are classified according to the Novo Nordisk classification of hypoglycaemia (see [Figure 17-1](#)) and the ADA classification of hypoglycaemia (see [Figure 17-2](#)).

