**Figure 17–2 ADA classification of hypoglycaemia**

### Hypoglycaemia during the pregnancy period

Data on treatment-emergent hypoglycaemic episodes with onset during the pregnancy period are presented in terms of the number of subjects with at least one event (N), the percentage of subjects with at least one event (%), the number of events (E) and the event rate per 100 years of exposure (R).

Protocol  
Trial ID: NN1250-4300  
UTN: U1111-1191-3018  
EudraCT no.: 2017-000048-17

~~CONFIDENTIAL~~

Date: 17 December 2020  
Version: 4.0  
Status: Final  
Page: 93 of 110

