**Novo Nordisk**

The endpoint will be summarised by treatment arm based on the in trial data. The number and percentage of subjects in each category will be displayed. The endpoint will further be summarised according to the following sub-groups:

- Subjects randomised as pregnant
- Subjects randomised as non-pregnant
- Subjects randomised as non-pregnant and exposed to trial drug at some point during the pregnancy period
- Subjects randomised as non-pregnant and not exposed to trial drug during the pregnancy period

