**Adverse events during the pregnancy period**

Adverse events will be coded using the most recent version of the Medical Dictionary for Regulatory Activities (MedDRA) database.

A treatment emergent AE (TEAE) is defined as an event that has onset date on or after the first day of exposure to randomised treatment and no later than 7 days after the last day of randomised treatment. If the event onset date is before the first day of exposure on randomised treatment and increases in severity at some point during the on-treatment period, then this event should also be considered as a TEAE. Major adverse cardiovascular events (MACEs, defined as all cardiovascular deaths, non-fatal myocardial infarctions and non-fatal strokes) are considered treatment-emergent until 30 days after the last day of randomised treatment.

Treatment emergent AEs are summarised descriptively. Data from TEAEs will be displayed in terms of the number of subjects with at least one event (N), the percentage of subjects with at least one event (%), the number of events (E) and the event rate per 100 years of exposure (R).

Adverse events with onset during the pregnancy period are defined as corresponding to the pregnancy period. Number of TEAEs during the pregnancy period will be summarised based on all subjects in SASpregnant.

Summaries of TEAEs and of serious TEAEs will be presented as an overview including all TEAEs, serious TEAEs, TEAEs by severity, TEAEs by relation to treatment and TEAEs leading to treatment discontinuation or withdrawal.

Furthermore, summary tables based on system organ class and preferred terms are made for:

- All TEAEs
- Serious TEAEs
- TEAEs possibly or probably related to trial product

Protocol  
 Trial ID: NN1250-4300  
 UTN: U1111-1191-3018  
 EudraCT no.: 2017-000048-17

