**Novo Nordisk**

**Table 4–3 Overview of defined data selections and observation periods**

Defined data selections or observation periods	Description
In-trial	
This represents the time period where subjects are considered to be in the trial, regardless of discontinuation of trial product.
 
The in-trial observation period starts at randomisation and ends at trial completion.
 
The date of trial completion is the date of the final scheduled follow-up visit V92.
 
For subjects not attending the follow-up visit V92, the date of trial completion will be the date of the last subject-investigator contact.

On-treatment	
This represents the time period where subjects are considered treated with the trial product.
 
It is a subset of the in-trial observation period, starting at the date of first dose of trial product and ending at the date of the last day on trial product.

Pregnancy period	
It is defined as the period from first day of pregnancy (date of conception corresponding to the first day in GW 2) or randomisation (whichever comes last) to the date of delivery.
 
The first day of pregnancy is based on the estimated gestational age from the US scan made before or at randomisation (visit 2) for subjects randomised pregnant and before or at visit 55 for subjects randomised non-pregnant and becoming pregnant in the conception period of the trial.
 
For subjects with delivery prior to the US scan the first day of pregnancy is determined by the investigator based on the estimated gestational age at the time of delivery.

Pre-pregnancy period	
It is defined for subjects randomised as non-pregnant. The period starts at randomisation (visit 2). Two different end-dates will be defined. For subjects who become pregnant the period ends at the day prior to first day of pregnancy. For subjects who do not become pregnant during the trial, the period ends at the same time as the in-trial period.

Post-pregnancy period	
This starts the day after the delivery and ends at the same time as the in-trial period.

The above definitions form the basis for combinations of periods. The on-treatment pregnancy period is e.g. the intersection between the on-treatment period and the pregnancy period.

Statistical Analysis Plan  
Trial ID: NN1250-4300  
UTN: U1111-1191-3018  
EudraCT No: 2017-000048-17

~~CONFIDENTIAL~~

Date: 27 January 2021  
Version: 2.0  
Status: Final  
Page: 15 of 34

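### Women who stopped trial insulin more than 7 days before conceiving stay in the denominator of the treatment-emergent pregnancy-period percentages, which understates those percentages, mainly in women randomised non-pregnant

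*SAP*

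**What the plan says.** **Membership.** SAP Table 4–2 defines SAS_pregnant as: "Includes all randomised women exposed to at least one dose of trial product and who are pregnant during the trial". Protocol 17.2 has the same rule. Neither requires the dose to fall in the pregnancy.

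**Treatment-emergent window.** For hypoglycaemia, Protocol 17.4.2.1 counts onsets "on or after the first day of trial product administration, and no later than 7 days from the last day on trial product". For adverse events, Protocol 17.4.2.2 uses a window ending "no later than 7 days after the last day of randomised treatment", extended to 30 days for major cardiovascular events.

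**What is displayed.** Under Protocol 17.4.2.1, "Data on treatment-emergent hypoglycaemic episodes with onset during the pregnancy period are presented in terms of the number of subjects" with at least one event, and also as "the percentage of subjects with at least one event", the event count and a rate per 100 years of exposure. Treatment-emergent adverse events are shown in the same four forms. Both use SAS_pregnant.

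**Rows.** SAP Table 5-6 reports hypoglycaemia separately for women randomised pregnant and non-pregnant. Its adverse-event row is by treatment arm only. Protocol 17.4.2.2 says in general terms that maternal safety data are also divided by pregnancy status at randomisation.

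**Stopping and staying.** Protocol 6.4 keeps women in the trial after they stop trial product. Protocol 8.3.3 covers those who stop in the conception period and conceive later.

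**Where the plan already separates these women.** For mode of delivery, Protocol 17.4.2.2 lists the subgroup "Subjects randomised as non-pregnant and not exposed to trial drug during the pregnancy period". Pregnancy outcomes and infant adverse events have matching splits (Protocol 17.4.2.3, SAP 5.4.3). SAP Table 4–3 also supplies the needed concept: "The on-treatment pregnancy period is e.g. the intersection between the on-treatment period and the pregnancy period".

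**The concern.** A woman may take trial insulin before pregnancy, stop, and conceive a month later. She meets the definition of SAS_pregnant, but her treatment-emergent window closed before her pregnancy period opened. She adds one to the denominator of each treatment-emergent percentage for that period and, apart from a major cardiovascular event within 30 days of stopping, can add nothing to the numerator. No passage removes her from that denominator. The plan clearly expects such women, since it gives them their own subgroup for mode of delivery and the infant endpoints.

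The error is in the reassuring direction, because the percentage with an event is too low. It falls on women randomised non-pregnant, the only group that can be on trial insulin during organogenesis (Protocol 5.5 and 6.7), and in a small denominator. The trial is open-label, so the share stopping before conception could differ between arms. In that case the comparison would be affected as well as the level.

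**Working it through.** **Inputs**

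- Planned randomisation (Protocol 17.1): 142 pregnant and 72 non-pregnant, with about 50% of the latter conceiving.
- Discontinuation (Protocol 17, missing data considerations for the primary estimand): at most 15% of women randomised non-pregnant and 10% of those randomised pregnant. These cover stopping at any time, not only before conception.
- Window: 7 days after the last day on product.

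**Plan's own figures.** With SD 0.85, margin 0.4% and 80% power, a t-based calculation gives 144 women delivering after GW 16. Then 144 / (0.9 × 0.9) = 177.8, stated as 178. The randomisation numbers agree: 142 + 0.5 × 72 = 142 + 36 = 178. The documents give no figure for stopping before conception.

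**Formula.** Let M be the women in the row and k those who stopped more than 7 days before conceiving. Then

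displayed % = (% among women who could have an event) × (1 − k/M),

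so the relative understatement is k/M. Only women randomised non-pregnant contribute to k.

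**All stops before conception.** k = 0.15 × 36 = 5.4.

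- Randomised non-pregnant: 5.4/36 = 15.0%. In whole women, 5/36 = 13.9% or 6/36 = 16.7%. With k = 5, a true 50.0% is shown as 50.0 × 31/36 = 43.1%.
- All women: 5.4/178 = 3.0%.
- By arm, M is about 36/2 = 18, so each such woman costs 1/18 = 5.6%.

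**Stops spread evenly (my assumption).** Take a constant hazard h over T weeks to conception, 38 weeks of pregnancy and 4 weeks post-partum, with 15% stopping in total: h = −ln(0.85)/(T + 42). The share stopping more than 7 days before conception is 1 − exp(−h(T − 1)).

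| T (weeks) | h per week | Understatement |
|---|---|---|
| 13 | 0.1625/55 = 0.00295 | 3.5% |
| 26 | 0.1625/68 = 0.00239 | 5.8% |
| 52 | 0.1625/94 = 0.00173 | 8.4% |

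Conception times uniform over 0–52 weeks also give 5.8%.

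**15% is not a strict bound.** It assumes that women who stop are as likely to conceive as the rest. If all 0.15 × 72 = 10.8 expected discontinuers were among the 36 who conceive, and all stopped beforehand, the figure would be 10.8/36 = 30%.

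**Between-arm comparison.** The ratio of percentages is multiplied by (1 − k₁/M₁)/(1 − k₂/M₂). Equal shares give 1. As an illustration, 2 of 18 against 3 of 18 gives (16/18)/(15/18) = 1.07.

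**The case against.** A one-dose safety set is conventional and these summaries are descriptive, with no test attached. The endpoints are numbers of episodes and events, and the counts are unaffected. Rates are not diluted either if exposure means on-treatment time, although the documents do not define it. All-episode hypoglycaemia tables, a full-analysis-set in-trial hypoglycaemia summary and all-SAE tables are also planned. Infant outcomes, on which exposure from conception bears most directly, are already split. Some women who stop early never enter the set: Protocol 6.5 withdraws those who start contraindicated medication before pregnancy or begin infertility treatment.

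These points stand and limit the importance. They do not repair the treatment-emergent percentages, and the companion tables answer a different question because they include drug-free pregnancies.

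Three stronger readings are tempting but unsupported:

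- **That the plan itself implies a ceiling of 14% or 15%.** The assumption covers stopping at any time, including during pregnancy and post-partum. The figure needs every stop to precede conception, and it could be exceeded.
- **That the arm comparison is biased.** This needs differential stopping before conception, for which the documents give no figure.
- **That pre-eclampsia and retinopathy percentages are diluted in the same way.** Neither is defined as treatment-emergent. The SAP moves the pre-eclampsia rate to years of observation, and the protocol also summarises retinopathy to the additional end-of-treatment visit. The question there is whether a drug-free pregnancy should be attributed to the arm.

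**Conclusion.** The mismatch between numerator and denominator is real and follows from the definitions. It affects treatment-emergent hypoglycaemia and adverse-event percentages for the pregnancy period, and nothing else in those tables with certainty. For adverse events, separate randomised-non-pregnant rows rest on the protocol's general statement, because the SAP row is by arm only.

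The size is not known from the documents. With 36 conceptions and the 15% assumption applied to them, the relative understatement in women randomised non-pregnant runs from about 3.5–8% (even spread of stops) to about 15% (all stops before conception). For all women it is at most about 3% on that basis. Planned numbers were used because SAP 6.3.1.1 gives 188 women in FAS_pregnant without the split by pregnancy status at randomisation.

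The effect is modest and descriptive, but it lowers a safety percentage and is easy to remove. The change should be made.

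**What to change.** 1. For treatment-emergent summaries of the pregnancy period, take as N the SAS_pregnant women whose treatment-emergent window overlaps that period: at least one dose in the pregnancy period or within the 7 days before it. The 7-day allowance is needed because a woman who stopped just before conception can still have a qualifying event.
2. Extend the exposed/not-exposed-in-pregnancy split from mode of delivery to the maternal hypoglycaemia and adverse-event tables.
3. Keep the full SAS_pregnant for the all-episode and all-SAE tables.
4. For pre-eclampsia and retinopathy, at most add the same split as a descriptive subgroup.

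The cost is SAP wording and flags derived from the first and last dates on trial product, which Protocol 8.5.15 already requires in the eCRF. N will differ slightly between tables, so a footnote is needed. The footnote should also say that women who stopped 1 to 7 days before conception are in N but fall in the not-exposed subgroup.
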